6.2 Glycemic control achievement rate (HbA1c)

(1) Patients to be tabulated and analyzed

Efficacy Analysis Set

(2) Details of tabulation and analysis

The Glycemic control achievement rate for HbA1c (NGSP value) will be tabulated ($< 7.0\%$, $\geq 7.0\%$ / $< 6.0\%$, $\geq 6.0\%$) and a bar graph will be created ($< 7.0\%$, $\geq 7.0\%$ / $< 6.0\%$, $\geq 6.0\%$) at each testing time point (start of Nesina treatment, 3 months, 6 months, 12 months, 18 months, 24 months, 30 months, and 36 months after Nesina treatment and last evaluation) (the unknown category will be excluded for the bar graph).

(3) Number of tables and figures

Table 6.2-1 and Figure 6.2-1

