## 7.0 Survey Methods

### 7.1 Observation Period

The observation period will be 36 months after the start date of Nesina treatment.

If Nesina treatment is discontinued for any reason, the survey will be ended at the discontinuation.

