#### 10.5.1 Changes in HbA1c over Time

The HbA1c values at each time point and the changes (values at each time point – values at the start of Nesina treatment) will be tabulated. The achieving percent in glycemic control for HbA1c will be tabulated for each time point.

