1.0 Definition of Terms and Handling of Laboratory/Measured Data

1.1 Definitions

Term	Definition
Nesina	Nesina tablet(s) is abbreviated as Nesina in this statistical analysis plan.
SOC	System Organ Class of MedDRA/J MedDRA/J version 20.1 is used for this document.
HLGT	High level group term of MedDRA/J
PT	Preferred term of MedDRA/J
LLT	Lowest level term of MedDRA/J
Registered patients	Patients whose registration was approved
Survey sheet (electronic) collected patients	Patients whose survey sheets were sent via CCI [REDACTED]
Survey sheet (electronic) uncollected patients	Of the registered patients, patients whose survey sheets (electronic) were uncollected.
Safety Analysis Set	Of the survey sheet (electronic) collected patients, patients who were evaluated for safety analysis. For tabulation, the description of “total” means the Safety Analysis Set.
Not Safety Analysis Set	Of the survey sheet (electronic) collected patients, patients who were excluded from safety analysis
Efficacy Analysis Set	Of the Safety Analysis Set, patients who were evaluated for efficacy analysis
Not Efficacy Analysis Set	Of the Safety Analysis Set, patients who were excluded from the efficacy analysis
First date of Nesina treatment	Of the start dates of the Nesina treatment period in patients, the earliest date is defined as the first date of Nesina treatment.
Last date of Nesina treatment	Of the last dates of the Nesina treatment period in patients, the latest date is defined as the last date of Nesina treatment. If Nesina treatment is continued and the year, month, and date of the continued treatment period are specified, the year, month, and date of the continued treatment period are defined as the last date of Nesina treatment. If the data for the year, month, and date of the continued treatment period are missing, the following date is defined as the last date of Nesina treatment. (1) First date of Nesina treatment + 3 years (same month and date), if Nesina treatment is continued based on the survey sheet (electronic) after 36 months of treatment* (2) For other than the above, the first date of Nesina treatment + 1 year (same month and date), if Nesina treatment is continued based on the survey sheet (electronic) after 12 months of treatment**

Term	Definition

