	For unknown onset date of adverse events (or adverse drug reactions, etc.), the onset period will be calculated as 1 day. However, if the start month and date of Nesina treatment are same as the onset month and date of adverse events (or adverse drug reactions, etc.), the onset period will be calculated as the start date of Nesina treatment.
Mild type 2 diabetes mellitus	Patients who have type 2 diabetes mellitus with HbA1c (NGSP value) of \leq 7.4% at the start date of Nesina treatment
Patients with diabetic complication	Patients with any of the following complications: diabetic nephropathy, diabetic retinopathy, or diabetic neuropathy.
Patients with diabetic nephropathy	Patients with complication of PT Code 10012660 (diabetic end stage renal disease) or 10061835 (diabetic nephropathy).
Patients with diabetic retinopathy	Patients with complication of PT Code 10012688 (diabetic retinal oedema) or 10012689 (diabetic retinopathy).
Patients with diabetic neuropathy	Patients with complication of PT Code 10012645 (diabetic autonomic neuropathy), 10012676 (diabetic mononeuropathy), or 10012680 (diabetic neuropathy).
Patients with concurrent hypertension	Patients with concurrent disease of the Standardised MedDRA Query (hereinafter SMQ) Code 20000147 (hypertension (SMQ) narrow).
Patients with concurrent dyslipidemia	Patients with concurrent disease of the SMQ Code 20000026 (dyslipidaemia (SMQ) narrow).
Patients with concurrent hyperuricemia	Patients with concurrent disease of the PT code meeting the Takeda MedDRA Query 20.1 (hereinafter, TMQ 20.1) (blood uric acid increased).
Patients with concurrent liver disorder	Patients with concurrent disease of the SMQ Code 20000005 (hepatic disorders (narrow)).
Patients with concurrent hepatic steatosis	Patients with concurrent disease of the PT Code 10019708 (hepatic steatosis).
Patients with concurrent alcoholic hepatitis	Patients with concurrent disease of the PT Code 10019728 (hepatitis alcoholic).
Patients with concurrent chronic hepatitis	Patients with concurrent disease of the PT Code 10008909 (chronic hepatitis).
Patients with concurrent hepatic cirrhosis	Patients with concurrent disease of the PT Code 10019641 (hepatic cirrhosis).
Patients with concurrent renal disorder	Patients with concurrent disease of the TMQ 20.1 (renal disease).
Patients with concurrent nephrotic syndrome	Patients with concurrent disease of the PT Code 10029164 (nephrotic syndrome).

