Concomitant medication (other)	Drugs other than the above (diabetic drugs, hypertension drugs, or dyslipidaemia drugs).
Protease Inhibitor	Use the results of the drug name in the survey sheet (electronic) coded with the NHI Drug List (Appendix 1. List of Protease Inhibitors).
Renal excretory drugs	Use the results of the drug name in the survey sheet (electronic) coded with the NHI Drug List (Appendix 2. List of Renal Excretory Drugs).
Nesina treatment period (days)	Actual treatment period from the start date to the end date of Nesina treatment. However, the washout period is excluded from the treatment period. Calculate using the following formula: End of Nesina treatment – start date of Nesina treatment + 1 (grand total). (Consider the washout period.)
Mean daily dose of Nesina	Calculate using the following formula: Total of “daily dose of Nesina × Nesina treatment period at the relevant dose” / Nesina treatment period. For the calculation of Nesina treatment period, refer to the above. If the daily dose of Nesina is a number outside specification in the survey sheet (electronic) and is actual number, use the relevant number.

Term	Definition
HbA1c (NGSP value)	
The NGSP value only will be used in this analysis.
 
For the HbA1c (JDS value), calculate using the following formula: $\text{NGSP value (\%)} = 1.02 \times \text{JDS value (\%)} + 0.25\%$ 
 
The HbA1c (international standard value) will be handled as the NGSP value.

Change in HbA1c	
For HbA1c converted to the NGSP value, calculate using the following formula: Laboratory value – Laboratory value at the start of Nesina treatment.

Glycemic control achievement rate	
Divide the following two categories for the Glycemic control achievement rate:
 
HbA1c (NGSP converted value) [Unit %] NGSP (%): < 6.0, ≥6.0 / < 7.0, ≥ 7.0

non-HDL cholesterol	
Calculate using the following formula: “Total cholesterol” – “HDL cholesterol.”

Summary statistics	
Number of patients, mean, standard deviation, minimum, first quartile, median, third quartile, and maximum.

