2.0 Disposition of Patients (Patient Diagram)

(1) Patients to be tabulated and analyzed

Registered patients

(2) Details of tabulation and analysis

The following will be tabulated: the number of registered patients, number of medical site at which patients is registered, number of patients whose survey sheets (electronic) are collected, number of patients whose survey sheets (electronic) are not collected, number of patients in the Safety Analysis Set, number of patients in the Not Safety Analysis Set, number of patients in the Efficacy Analysis Set, and number of patients in the Not Efficacy Analysis Set.

For the number of medical sites at which patients are registered, do not duplicate the same medical site with different departments.

For patients whose survey sheets (electronic) are not collected, tabulate the number of patients for each reason for not collected survey sheets.

For the Not Safety Analysis Set and Not Efficacy Analysis Set, the number of patients will be tabulated for each reason for exclusion to create the list.

The following is the handling of the decision whether patients who meet the following criteria should be evaluated:

Criterion	Safety evaluation	Efficacy evaluation
Pre-agreement administration [found after administration]	×	×
Registration 15 days after the start of Nesina treatment [found after registration]	×	×
Nesina taking not confirmed [after the end of patient registration period]	×	×
No data for post-administration of Nesina	×	×
Data reliability was not confirmed	×	×
Other than patients with mild type 2 diabetes mellitus	○	×

○ Included, × Excluded or not evaluated

(3) Number of tables and figures

Figure 2.0-1 and Table 2.0-1

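### SAP 6.2 does not state the table denominator for the HbA1c achievement rate and gives no start rate for the patients measured at each later visit

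*SAP*

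**What the plan says.** Protocol 10.5.1 names two HbA1c outputs. One is the change from start; for the other, "The achieving percent in glycemic control for HbA1c will be tabulated for each time point". Protocol 10.5.2 stratifies both at 36 months.

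SAP 6.2 tabulates the rate at the 7.0% and 6.0% cut-offs in the Efficacy Analysis Set. The time points are start, 3, 6, 12, 18, 24, 30 and 36 months, and last evaluation. A bar graph is added, for which "the unknown category will be excluded for the bar graph". Nothing comparable is said for the table. The definition in SAP 1.1 reads "Divide the following two categories for the Glycemic control achievement rate" and then lists the cut-offs. It has no unknown category and no denominator.

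The Efficacy Analysis Set is "Of the Safety Analysis Set, patients who were evaluated for efficacy analysis". In the current SAP 2.0, the only exclusion that applies to efficacy alone is "Other than patients with mild type 2 diabetes mellitus". SAP 1.1 defines mild disease as "Patients who have type 2 diabetes mellitus with HbA1c (NGSP value) of" at most 7.4% at the start date. No later HbA1c is required.

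On follow-up, Protocol 7.1 says "The observation period will be 36 months after the start date of Nesina treatment", and also "If Nesina treatment is discontinued for any reason, the survey will be ended at the discontinuation". SAP 1.5 does not use 12- and 36-month values from patients who had discontinued.

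**The concern.** Two gaps meet in one output.

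First, the instruction on the unknown category covers the graph only. A programmer could reasonably divide by everyone in the set for the table and by patients with a value for the graph. The same rate would then appear with two values.

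Second, membership of the set rests on the start HbA1c, so essentially every member counts in the start rate. A later rate can classify only those still on treatment and measured. The HbA1c change in SAP 6.1 is paired within patient; the achievement rate is not, and no start rate is planned for the patients who remain.

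This is a 36-month survey without a comparator, and readers will set the start rate against the 36-month rate. Part or all of any difference could reflect who stayed.

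**Working it through.** **The plan's own figures.** The documents give no expected achievement rate or dropout rate, so there is no planned figure for this output to reproduce. One related figure can be checked. The inclusion limit of JDS 7.0% (Protocol 4.1) converts by the SAP 1.1 formula to 1.02 × 7.0 + 0.25 = 7.39, which agrees with the NGSP limit of 7.4% for mild disease. Entry to the efficacy set therefore does turn on the start HbA1c.

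**Step 1: table against graph.** Let r be the rate among patients with a value at a visit, and u the share of the set without one.

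- Unknown excluded: r
- Unknown kept in the denominator: r × (1 − u)
- Gap: r × u

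With r = 60% (assumed):

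| u | Unknown excluded | Unknown in denominator | Gap (points) |
|---|---|---|---|
| 5% | 60.0% | 57.0% | 3.0 |
| 10% | 60.0% | 54.0% | 6.0 |
| 30% | 60.0% | 42.0% | 18.0 |
| 50% | 60.0% | 30.0% | 30.0 |

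The gap arises only if the table uses the whole set. The SAP does not say which it uses.

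**Step 2: start against later visit, with no patient changing class.** Let p be the share at goal at start, a the retention of patients at goal, and b the retention of the others.

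- Later rate, unknown excluded: pa / (pa + (1 − p)b)
- Later rate over the whole set: pa

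With p = 60% (assumed), so the start rate is 60%:

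| a | b | Unknown excluded | Whole set |
|---|---|---|---|
| 70% | 70% | 60.0% | 42.0% |
| 75% | 55% | 67.2% | 45.0% |
| 80% | 40% | 75.0% | 48.0% |
| 55% | 75% | 52.4% | 33.0% |

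For the second row: 0.60 × 0.75 = 0.45; 0.40 × 0.55 = 0.22; 0.45 / 0.67 = 67.2%.

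The same formulas were run for p = 40%, 60% and 80%, with the four retention pairs above and 70%/60%. The rate with unknown excluded shifted by −7.6 to +17.1 points, and by 0 when retention was equal. A whole-set rate fell by 8 to 36 points in every case.

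**Step 3: the remedy in the same scenarios.** Among patients with both values, the start rate is also pa / (pa + (1 − p)b), because no one changed class. Printed beside the visit rate it is identical, so the spurious change is 0 in every row.

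**The case against.** The strongest reply is that the text does not establish two denominators. The SAP 1.1 definition has no unknown category, so a table could list unknown as a count and base its percentages on known values. SAP 6.1 and 6.3 also exclude the unknown category from bar graphs of changes. A missing value could not enter a mean change in any case, so the phrase may be only a display instruction. This stands. A reader might infer that every missing value lowers the tabulated rate, and that table and graph will move in opposite directions. The documents support only that the table denominator is unstated. Opposite directions would also require selection in a particular direction.

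A reader might also infer that start and later rates come from different people, or that attrition by itself must move the rate. Later patients are a subset of the start patients. With unknown excluded, the rate moves only when retention depends on glycemic control. Nothing in the documents shows that it does. The efficacy set stops at 7.4%, so at the 7.0% cut-off the patients not at goal at start lie only between 7.0% and 7.4%. A 20-point retention gap across so narrow a band is an assumption.

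Two planned outputs help. SAP 6.4(v) splits the rate by start HbA1c at 6.0% and 7.0%, the goal cut-offs themselves. With unknown excluded and no true change, each stratum would stay at 100% or 0%, which exposes a selection effect. Last evaluation classifies patients who left early by their last value. Both reduce the concern, but neither changes the start and 36-month figures printed in 6.2, and 6.4 states no denominator either.

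Finally, the rate is descriptive. No test is attached to it, so no error rate or sample size is affected.

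**Conclusion.** The point holds in a limited form. SAP 6.2 leaves the table denominator open, which allows a table–graph gap of r × u (18 points at 60% and 30%). It also compares a start rate over essentially the whole set with later rates over the retained subset, so a difference can appear with no within-patient change if retention depends on control. In the illustration the rate goes from 60% to 67%; with equal retention it stays at 60%, and with the reverse selection it falls to 52%.

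All rates and retentions here are assumed. Neither the direction nor the size of any real shift can be taken from the documents. The reason to act is that the output is named in the protocol, the start-to-36-month comparison is the obvious reading of it, and a better version comes from data already collected.

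**What to change.** In SAP 6.2, and for the rates in 6.4 and 6.5:

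- At each visit, use as denominator the patients with an HbA1c both at start and at that visit, in the table and the graph alike.
- Print the start rate of those same patients beside the visit rate.
- Show unknown as a count only, outside the percentages.
- Keep the last-evaluation rate alongside. The paired rate still describes only retained patients and does not repair attrition.

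The cost is a few lines of SAP wording, a denominator rule in the programming and one extra column. No new data are needed.

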6.3 Changes in Fasting blood glucose level and Fasting insulin level

(1) Patients to be tabulated and analyzed

Efficacy Analysis Set

(2) Details of tabulation and analysis

For fasting blood glucose level and fasting insulin level, summary statistics will be calculated at each testing time point (start of Nesina treatment, 3 months, 6 months, 12 months, 18 months, 24 months, 30 months, and 36 months after Nesina treatment and last evaluation). For changes, summary statistics and the mean 95% confidence intervals will be calculated and the paired t-test will be performed.

Measured values of fasting blood glucose level and fasting insulin level will be plotted and for

the changes a bar graph will be created excluding the unknown category at each testing time point (start of Nesina treatment, 3 months, 6 months, 12 months, 18 months, 24 months, 30 months, and 36 months after Nesina treatment and last evaluation).

(3) Number of tables and figures

Tables 6.3-1 and 6.3-2 and Figures 6.3-1 and 6.3-2

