## 1.0 Surveillance Background

The goal of diabetes mellitus treatment is to maintain patients' QOLs as those in healthy people and to secure their lifetimes through management for a favorable blood glucose level for a long time. In particular, early drug treatment is considered important for patients with mild type 2 diabetes mellitus, which maintains a favorable blood glucose level and inhibits the diabetes progress, along with prevention of microangiopathy.

As an oral drug started to be administered early to patients with mild type 2 diabetes mellitus, the desirable drug should have a low risk of hypoglycemia, be well tolerable, and not exhaust pancreatic function.

DPP-4 inhibitors selectively inhibit DPP-4, increase blood GLP-1 levels, and prompt the pancreas to secrete insulin in a glucose level-dependent manner. Taken together, DPP-4 inhibitors are expected to be highly effective for patients with mild type 2 diabetes mellitus. As a DPP-4 inhibitor, Nesina tablets (generic name: alogliptin benzoate) are confirmed to be highly effective and safe when administered alone and combined with various oral diabetic drugs in clinical studies conducted in Japan. The following are approved indications for Nesina:

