#### 4.1 Inclusion Criteria

Patients who meet the following criterion will be included in this Surveillance:

- (1) Patients with HbA1c (JDS value)  $\leq 7.0\%$  at the time of enrolment (within 3 months before initiation of Nesina therapy)  
\* Regardless of the use of antidiabetic medication

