α-glucosidase inhibitors	Drugs of the NHI Drug List Code starting with 3969003, 3969004, 3969009, or 3969102.
Thiazolidines	Drugs of the NHI Drug List Code starting with 3969005, 3969007, 3969100, 3969101, or 3969103.
Sulfonylureas	Drugs of the NHI Drug List Code starting with 3961 or 3969101.
Biguanides	Drugs of the NHI Drug List Code starting with 3962, 3969100, 3969104, or 3969105.
Rapid-acting insulin secretagogues	Drugs of the NHI Drug List Code starting with 3969006, 3969008, 3969013, or 3969102.
Insulin preparations	Drugs of the NHI Drug List Code starting with 2492.
DPP-4 inhibitors	Drugs of the NHI Drug List Code starting with 3969010, 3969011, 3969012, 3969014, 3969015, 3969016, 3969017, 3969024, 3969025, 3969103, 3969104, or 3969105.

Term	Definition
GLP-1 receptor agonists	Drugs of the NHI Drug List Code starting with 2499410, 2499411, 2499415, or 2499416.
SGLT2 inhibitors	Drugs of the NHI Drug List Code starting with 3969018, 3969019, 3969020, 3969021, 3969022, or 3969023.
Combination of diabetic drugs	Drugs of the NHI Drug List Code starting with 3969100, 3969101, 3969102, 3969103, 3969104, or 3969105.
Other diabetic drugs	Other diabetic drugs not classified into the above diabetic drug categories (α -glucosidase inhibitors, thiazolidines, sulfonylureas, biguanides, rapid-acting insulin secretagogues, insulin preparations, DPP-4 inhibitors, GLP-1 receptor agonists, SGLT2 inhibitors, or combination of diabetic drugs).

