1.4 Level of Significance and Confidence Coefficient

Two-sided 5%, two-sided 95%.

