6.4 Changes in HbA1c, etc. by Factor Probably Affecting Efficacy

(1) Patients to be tabulated and analyzed

Efficacy Analysis Set

(2) Details of tabulation and analysis

For changes in HbA1c (NGSP values), summary statistics and the mean 95% confidence intervals will be calculated and the paired t-test will be performed at each testing time point (start of Nesina treatment, 3 months, 6 months, 12 months, 24 months, and 36 months after Nesina treatment and last evaluation).

The Glycemic control achievement rate for HbA1c ($< 7.0\%$, $\geq 7.0\%$ / $< 6.0\%$, $\geq 6.0\%$) at each testing time point (start of Nesina treatment, 3 months, 6 months, 12 months, 24 months, and 36 months after Nesina treatment and last evaluation) will be tabulated at the following parameters:

i Sex (Male, Female)

ii Age (< 65 years, ≥ 65 years)

iii Age (< 75 years, ≥ 75 years)

iv Concurrent renal disorder (No, Yes)

v HbA1c (NGSP value) at the start of Nesina treatment ($< 6.0\%$, 6.0% to $< 7.0\%$, 7.0% to $< 8.0\%$, $\geq 8.0\%$)

vi Mean daily dose of Nesina (> 25 mg, 25 to > 12.5 mg, 12.5 to > 6.25 mg, or 6.25 mg)

vii Concomitant diabetic drugs (α -glucosidase inhibitors, thiazolidines, sulfonylureas, biguanides, rapid-acting insulin secretagogues, or insulin preparations)

(3) Number of tables and figures

Tables 6.4-1 to 6.4-14

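### SAP 6.3 tests the change in fasting insulin only with insulin-treated patients included; a split by insulin use at the two visits would make the table readable

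*SAP*

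**What the plan says.** SAP 6.3 takes the Efficacy Analysis Set as its population and states: "For fasting blood glucose level and fasting insulin level, summary statistics will be calculated at each testing time point". The time points run from the start of treatment to 36 months, plus the last evaluation. For the change it adds: "For changes, summary statistics and the mean 95% confidence intervals will be calculated and the paired t-test will be performed". SAP 1.4 sets the level at two-sided 5%. Section 6.3 reads the same in all three SAP versions supplied.

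Protocol 4.1 admits patients with HbA1c (JDS) of at most 7.0%, with the note "Regardless of the use of antidiabetic medication". None of the exclusion criteria in Protocol 4.2 concerns insulin use.

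The SAP provides for insulin users. SAP 1.1 defines insulin preparations as "Drugs of the NHI Drug List Code starting with 2492". SAP 4.0 tabulates them as prior and as concomitant drugs, and SAP 5.4.1 and 5.17 use them as a stratum for adverse drug reactions. SAP 6.4 item vii uses them as a stratum for HbA1c; its list of concomitant drug classes ends with "rapid-acting insulin secretagogues, or insulin preparations".

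**The concern.** A fasting insulin reading taken while a patient uses an insulin preparation may contain injected insulin as well as the patient's own. Of the efficacy measures in the SAP, it is the only one that a co-medication can enter directly as the measured substance. A patient who starts insulin during the 36 months could show a rise that is not secretion, and one who stops it could show a fall.

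What is at stake is interpretation. Protocol 1.0 says of the drug class that it acts to "prompt the pancreas to secrete insulin in a glucose level-dependent manner", and it wants an early oral drug not to exhaust pancreatic function. Against that background, a reader who finds a fasting insulin table under efficacy is likely to take it as the patient's own insulin. As planned, such a reader could not tell how much of the mean change comes from patients whose injected insulin changed, because no table leaves them out and none gives their number.

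**Working it through.** **1. Can insulin users be in the analysed set?** Yes. Entry does not depend on antidiabetic medication (Protocol 4.1). The SAP 2.0 disposition table removes nobody for insulin use; in the current version its only efficacy-only exclusion is disease that is not mild. Under Protocol 7.1 the survey ends early only when Nesina is discontinued, so starting insulin does not end observation.

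**2. Does any other rule or table separate them?** No. SAP 1.5 has no rule for values taken on insulin, and its last evaluation is simply the last visit, so insulin started late enters that row too. SAP 6.4 and 6.5 stratify the HbA1c change and the HbA1c achievement rate only.

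**3. Do the documents give their number?** No. The only size calculation is in Protocol 3.2 and concerns adverse drug reactions. It reproduces: ln(0.05)/ln(1 − 0.005) = 597.6, so 598 patients, or 3/0.005 = 600 by the rule of three, against the stated 600. The same section counts five regimens in the target population: 1864 + 226 + 175 + 273 + 109 = 2647 of 4165. That leaves 4165 − 2647 = 1518 patients (1518/4165 = 36.4%) on other regimens. How many of them used insulin is not stated.

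**4. How large could the effect be?** The documents supply no input, so this is an illustration. Assume that the patient's own insulin does not change on average, that the SD of that change is 5 µU/mL, and that in a net share f of pairs injected insulin shifts the change by D in one direction. The number of pairs N is also assumed.

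- Spurious mean change: m = f × D
- SD of change: √(5² + f(1 − f)D²)
- Standard error: SE = SD/√N
- Chance of a significant result: Φ(m/SE − 1.96) + Φ(−m/SE − 1.96)

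Worked case, f = 1%, D = 10, N = 1000: m = 0.01 × 10 = 0.10; SD = √(25 + 0.0099 × 100) = 5.10; SE = 5.10/√1000 = 0.161; m/SE = 0.62; chance = 9.5%.

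| f | D (µU/mL) | m (µU/mL) | SD | Chance, N = 1000 | Chance, N = 5000 |
|---|---|---|---|---|---|
| 0.5% | 5 | 0.025 | 5.01 | 5.3% | 6.4% |
| 1% | 10 | 0.10 | 5.10 | 9.5% | 28.4% |
| 2% | 10 | 0.20 | 5.19 | 23.0% | 77.7% |
| 5% | 10 | 0.50 | 5.45 | 82.6% | about 100% |
| 5% | 20 | 1.00 | 6.63 | 99.8% | about 100% |

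The nominal chance is 5%. At the low end the effect is negligible. At the high end the test would usually be significant with no change in the patient's own insulin. The documents do not say where in this range the survey lies. If some patients start insulin and others stop it, the shifts offset and the net effect is smaller.

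**5. Are the data for a split available?** Yes. Protocol 9.3 collects the name, daily dose, route and administration period of other diabetic drugs. Protocol 9.4 lists no sampling date, so use has to be aligned to the nominal visit.

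**The case against.** The strongest objection is that the plan makes no error on its own terms. Protocol 10.5 names only HbA1c under efficacy. Fasting insulin appears in Protocol 9.4 as one laboratory item, and nowhere do the documents say that it measures pancreatic secretion. The objective is safety and efficacy in routine practice, so describing values under whatever co-medication patients take is legitimate. This stands, and it is why the all-patient table should stay.

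Second, insulin users may be very few. The indication quoted in Protocol 1.0 covers diet and exercise plus four oral classes, the disease is mild, and Protocol 3.2 plans no insulin group. A drug-code row shows that a group was foreseen, not that it is large. This also stands.

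Third, a stable injected dose partly cancels in a paired change. That limits the effect on the test to pairs in which insulin was started, stopped or re-dosed. Levels at each visit remain mixed in any case.

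Three stronger readings are tempting, and the documents support none of them:

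- A reader might infer that the planned result is biased by a material amount. Share, shift, SD and assay are all missing, and the assay determines how far injected insulin enters the reading at all. The 0.1 µU/mL in SAP 1.6 is a display digit, so exceeding it does not show materiality.
- A reader might infer that all insulin-treated patients distort the test. The third point above answers that.
- A reader might infer that values taken on insulin should simply be dropped. That selects on a post-baseline event: patients who came to need insulin leave the late visits, which could make the patients' own insulin look better preserved. It also leaves the last evaluation undefined.

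**Conclusion.** The point holds as a gap in presentation that is cheap to close. SAP 6.3 paired-tests fasting insulin in a set that can include insulin users, and no planned table shows the result without them, although the SAP makes that separation for HbA1c and adverse drug reactions. For pairs in which insulin was started, stopped or re-dosed, the change may partly reflect injected insulin.

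Its size is unknown. The illustrated range of 0.025 to 1.0 µU/mL rests wholly on assumed shares, shifts, SD and numbers of pairs, and the true effect may be near the bottom of it or smaller. It is confined to the fasting insulin outputs; the planned sample size and the fasting glucose, HbA1c and safety analyses are unaffected. Even with the split, a single-arm survey with sulfonylureas and rapid-acting secretagogues in use cannot attribute the change to Nesina alone.

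**What to change.** In SAP 6.3:

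- Keep the fasting insulin table for all patients in the Efficacy Analysis Set.
- Add the same summary statistics, 95% interval and paired t-test for pairs with no insulin preparation (code 2492) in use at either the start or the later visit.
- Report the remaining pairs in a separate row with their n.
- Determine use from the recorded administration periods, aligned to the nominal visit. Do not use the SAP 1.1 definition of concomitant medication, which counts any use after the start of treatment.
- Classify the last evaluation by insulin use at that visit, without substituting an earlier value.
- Base any statement about the patient's own insulin on the no-insulin rows, and state beside them that patients who needed insulin leave these rows at late visits.

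The cost is a few sentences in SAP 6.3, some extra table rows and a date comparison on data already collected. The downsides are the post-baseline selection just named and slightly fewer pairs in the added rows.
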